8.3 Protocol deviations

Major deviations (as defined in section 6.6) will be summarized by cohort.

Protocol deviations identified on protocol deviation Logs from ICON Medical will be listed, including the classification of major and minor deviations. The inclusion/exclusion criteria violated at Pre-screening and at Screening visits will be also listed.

8.4 Demographics and baseline characteristics

8.4.1 Demographics

The following demographic parameters will be summarized descriptively or by using frequencies on FAS:

- Age.
- Sex.
- Race.
- Ethnicity.
- Female of childbearing potential.
- Height at baseline.
- Weight at baseline.
- Body mass index (BMI) at baseline.
- Eastern Cooperative Oncology Group (ECOG) performance status at baseline.
- Electrocardiogram (ECG) interpretation at baseline.
- Systolic blood pressure (mmHg) at baseline.
- Diastolic blood pressure (mmHg) at baseline.
- Heart rate (beats/min) at baseline.
- Respiratory rate (breaths/min) at baseline.
- Temperature (°C) at baseline.

8.4.2 Baseline and disease characteristics

The following baseline and disease characteristics parameters will be summarized descriptively or by using frequencies on FAS:

- Time since initial diagnosis (months).
- Cancer type.
- Cancer sub-type (only for PTCL subjects).
- CD30 expression level (only for PTCL subjects) (using categories: $\geq 1\%$ to $< 5\%$, $\geq 5\%$ to $< 10\%$, $\geq 10\%$ to $< 50\%$, $\geq 50\%$).
- Ann Arbor stage and Ann Arbor stage extension at initial diagnosis (only for PTCL subjects).
- Ann Arbor stage and Ann Arbor stage extension at Screening (only for PTCL subjects).
- TNMB staging at baseline (only for TMF subjects).
- Laboratory parameters:
 - o Alanine transaminase (ALT).
 - o Aspartate transaminase (AST).
 - o Lactate dehydrogenase (LDH).
 - o Albumin.
 - o Total bilirubin.
 - o Creatinine.

- C-reactive protein (CRP).
- Platelet count.
- Hemoglobin.
- White blood cells (WBC).
- Absolute neutrophils.
- Absolute monocytes.
- Absolute lymphocytes.
- Absolute eosinophils.
- Absolute basophils.
- Modified Severity Weighted Assessment Tool (mSWAT) total score.
- Composite Assessment of Index Lesion Severity (CAILS) total score.
- Prior systemic therapies (yes/no).
- Prior cancer surgeries (yes/no).
- Prior radiation therapies (yes/no).

These parameters and some other baseline and disease characteristics parameters will be listed for the FAS.

8.4.3 Medical history

A summary of medical history will be presented by system organ class (SOC) and preferred term (PT) coded using Medical Dictionary for Regulatory Activities (MedDRA) version 22.0 or higher on the FAS.

Medical history findings will be also listed.

8.4.4 Prior and concomitant medications

Medications used in this study will be coded by using the latest available version of the World Health Organization Drug Dictionary Enhanced (WHODDE) (March 2019 or later).

Prior medications are defined as those medications with a start date prior to the first dose of study drug.

Concomitant medications are defined as those medications with a start date on or after the first dose of study drug.

Prior and concomitant medications will be summarized separately using frequency tables by ATC class (ATC Level 2) and preferred name by cohort on FAS.

A listing will be also provided for subjects' prior and concomitant medications.

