6.9.1 Acceptable Concomitant Medications

All treatments and supportive care that the Investigator considers necessary for a subject's welfare may be administered at the discretion of the Investigator in keeping with the study site's standards of medical care except for the prohibited concomitant medications listed in [Section 6.9.2](#). All concomitant medication will be recorded in the eCRF including all prescription, over-the-counter, herbal supplements, and iv medications and fluids. If changes occur during the trial period, documentation of drug dosage, frequency, route, and date may also be included in the eCRF. All concomitant medications received within 30 days before the first dose of study drug and 30 days after the last dose of study drug should be recorded. Concomitant medications administered >30 days after the last dose of study drug should be recorded for serious adverse events (SAEs) that are considered related to study drug ([Section 7.10](#)).

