8.4 Concomitant Medication

Concomitant medication and significant non-drug therapies after the start of study drug will be listed and summarized by WHO ATC terms in contingency tables.

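### SAP 8.4.4 leaves drugs already being taken at first dose, and continued on AFM13, out of the concomitant medication table

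*SAP*

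**What the plan says.** SAP 8.4.4 gives two definitions. For prior medication: "Prior medications are defined as those medications with a start date prior to the first dose of study drug". For concomitant medication: "Concomitant medications are defined as those medications with a start date on or after the first dose of study drug". It then states how they are reported: "Prior and concomitant medications will be summarized separately using frequency tables by ATC class (ATC Level 2) and preferred name by cohort on FAS". It adds: "A listing will be also provided for subjects' prior and concomitant medications".

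The protocol treats the subject in two places. Section 8.4, on analysis, says: "Concomitant medication and significant non-drug therapies after the start of study drug will be listed and summarized by WHO ATC terms". Section 6.9.1, on data collection, covers "All concomitant medications received within 30 days before the first dose of study drug and 30 days after the last dose of study drug". It also asks for medications given later than that to be recorded when they relate to a serious adverse event attributed to study drug.

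**The concern.** The SAP rule looks at when a drug was started and never at when it was stopped. A reader of a concomitant medication table expects it to show what subjects were taking while on study drug. Under this rule it shows only what they began once treatment had started. Long-running co-medication present at first dose is placed in the prior table, where it is mixed with drugs that were stopped before dosing.

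What is at stake is the description of background medication against which the safety results are read. No estimate or test depends on it.

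**Working it through.** No figure in the plan bears on this point, so the check is one of logic, followed by a formula for the size.

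**Step 1. Classify every possible record.** Let S be the start date, E the stop date and D1 the date of first AFM13 dose.

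| Record | Taken on or after D1? | SAP 8.4.4 table |
|---|---|---|
| (a) S < D1 and E < D1 | No | Prior |
| (b) S < D1 and E ≥ D1, or ongoing | Yes | Prior only |
| (c) S ≥ D1 | Yes | Concomitant |

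Medication taken on or after first dose is (b) plus (c). The concomitant table contains (c) alone. The two definitions are mutually exclusive, and no visible text adds an ongoing category or counts a record twice.

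**Step 2. Compare with the protocol.** Section 6.9.1 defines its window by receipt, so class (b) records are collected. Section 8.4 describes medication in the period from the start of study drug. The natural reading is medication taken in that period, which is (b) plus (c), although the wording could also be read as medication started in it, which is (c).

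**Step 3. Check whether the SAP can identify class (b).** SAP 8.5.2 links a once-weekly premedication record to an infusion visit when the span of its intake dates covers the infusion date. That is an overlap rule, so the SAP already relies on intake intervals. It feeds only the premedication summaries, not the table in 8.4.4.

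**Step 4. Size.** Take one row of the concomitant table (an ATC class or a preferred name). Let U be the number of subjects using it on treatment, and f the fraction of them whose only records in that row began before D1.

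Subjects shown = U × (1 − f)

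The values of f below are assumptions, since the documents give none:

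| f | Share of true users shown |
|---|---|
| 0.1 | 1 − 0.1 = 90% |
| 0.3 | 1 − 0.3 = 70% |
| 0.5 | 1 − 0.5 = 50% |

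Because f cannot be negative, the start-date rule can only lower the count of use from first dose onward. A row is correct only when f = 0. A subject who has a class (b) record and also a class (c) record in the same row is still counted, so f is smaller than the share of users with any ongoing record.

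**The case against.** The strongest reply is that this is a matter of labelling. Nothing is lost: ongoing drugs appear in the prior table by class and name and in the subject listing. Where co-medication matters most in the SAP's own analyses, it has separate handling. SAP 8.5.2 summarizes premedication by visit, using the drug administration page as well as medication records, and relates infusion interruption to steroid, antihistamine and analgesic intake. SAP 8.7.1 tabulates steroid premedication against infusion-related reactions. No visible rule for response rate or duration of response draws on the 8.4.4 table. Protocol 8.4 is open to a started-after reading, and Protocol 6.9.1 is a collection rule, not an analysis definition. The pages of SAP section 7, which covers derived variables and incomplete dates, are not shown in the public copy.

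Most of this stands and limits the point to a descriptive one. It does not remove it. The prior table cannot stand in for the missing rows because it does not separate classes (a) and (b). The premedication analyses do not cover other drugs ongoing at first dose. SAP 8.4.4 is complete on its face and refers to no other rule that would change it.

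**Conclusion.** The point holds as a minor descriptive error. As defined, the concomitant table omits drugs started before first dose and continued on AFM13, and so can only understate on-treatment use of non-study medication. The amount cannot be determined from the documents. The conclusion rests on the visible text of 8.4.4 and on the natural, though not the only, reading of Protocol 8.4.

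A reader might infer more, and four stronger readings are not supported:

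- **That most chronic co-medication is missed.** No document gives the share of drugs ongoing at first dose.
- **That ongoing corticosteroids would distort the reading of response.** The documents do not state a link between steroids and lymphoma response. The list of prohibited medications in Protocol 6.9.2 is redacted, so it is not known how much ongoing steroid use was allowed.
- **That AFM13 exposure is understated.** That is derived separately in SAP 8.5.1 and is unaffected.
- **That the SAP plainly contradicts the protocol.** Protocol 8.4 is ambiguous between taken and started.

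Response rate, duration of response and the binomial tests do not change.

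**What to change.** Amend SAP 8.4.4 as follows:

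- **Concomitant:** any medication taken on or after first dose, through 30 days after last dose. This means started on or after first dose, or started before it and either ongoing or stopped on or after it.
- **Later medications:** those recorded beyond 30 days for related serious adverse events, as Protocol 6.9.1 requires, are listed separately. The present definition has no end date and would mix them in.
- **Prior:** keep as started before first dose, and state that a drug meeting both definitions is counted in both tables.
- **Missing stop dates:** handle them consistently with SAP 7.2.2. If that section has no rule, treat the drug as ongoing.

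The cost is a few sentences and one programming condition. No new data are needed, since the protocol already collects medication by receipt. The change should be made before database lock.

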8.4.5 Prior anti-cancer medications

Prior systemic therapies, prior cancer surgeries and prior radiation therapies will be summarized by cohort on FAS.

For prior systemic therapies, the following data will be summarized:

- Subjects with at least one prior systemic therapy.
 - Number of treatment lines.
 - Time between end of last treatment to study start (months).
 - Medication type.
 - Best overall response.
 - Best response to Brentuximab vedotin (preferred term = 'BRENTUXIMAB VEDOTIN').
 - Reason for discontinuing systemic therapy.
 - Systemic therapies classified by WHODDE ATC class (ATC Level 2) and preferred name.
- Transplants and non-transplant therapies will be summarized separately.

Prior cancer surgeries will be summarized by MedDRA SOC and PT.

For prior radiation therapies, the following data will be summarized:

- Subjects with at least one prior radiation therapy.
- Number of prior radiation therapies.
- Time between end of last radiation therapy to study start (months).
- Type of radiation therapy.
- Intent.
- Settings.
- Best overall response to radiation therapy.

8.5 Exposure to study treatment

8.5.1 AFM13 study drug

The following parameters, relative to AFM13 drug administration, will be calculated and summarized by cohort using descriptive statistics for the FAS:

- Number of infusions of AFM13.
- Dose exposure (weeks).
- Cumulative dose (mg).
- Dose intensity (mg/week).
- Relative dose intensity (%).

Final Analysis Statistical Analysis Plan (SAP)

The number of infusions with interruptions and dose modifications (including the reasons) will be also summarized by cohort. The number of subjects who take the 200 mg dose during the entire study will be also summarized (see Section 8.8.5).

Listing will be provided for AFM13 administration and exposure.

8.5.2 Premedications

The following medications taken before each AFM13 study drug administration will be listed and summarized:

- H1 antihistamine/H2 antagonist/Antihistamine.
- Analgesic/Fever reducer..
- Nonsteroidal anti-inflammatory drugs (NSAIDs).
- Glucocorticoid/Corticosteroid.
- Other.

NSAIDs and “other” medications are selected based on a list of ATCs and/or preferred names that Sponsor will provide. For - H1 antihistamine/H2 antagonist/Antihistamine, Analgesic/Fever reducer and Glucocorticoid/Corticosteroid categories, Sponsor will also provide the list of ATCs and/or preferred names but this will be also based on the study drug administration CRF page questions relative to antihistamine, acetaminophen and dexamethasone (or equivalent steroid) intakes.

These premedications will be summarized by visit. The medications collected during the study (in the prior and concomitant medications CRF pages) are not collected related to a specific visit. Consequently, the following rule will be used to associate the premedications to a visit:

If premedication start date = Cycle X Day Y drug administration, the medication will be associated to the visit Cycle X Day Y. To be considered as a premedication, the indication of use should be “Other” or “Condition under study” or “Prophylaxis”.

For premedications which are recorded only once during the study in the CRF (recorded with frequency = Once weekly), if the medication intake dates include the study drug administration date, the medication the medication will be associated to the study drug administration visit.

To evaluate the relationship between dose intakes and pre-medications, an overall shift table will be generated between the following data to summarize the number of infusions received in each category (ie, number of infusions where the dose administered was > 0 mg):

- Infusion interrupted (Yes/No)

- H1 antihistamine/H2 antagonist/Antihistamine intake (Yes/No)
- Analgesic/Fever reducer intake (Yes/No)
- Glucocorticoid/Corticosteroid intake (Yes/No).

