8.7.1 Adverse events

All Adverse events (AEs) will be classified by SOC and PT according to the MedDRA Version 22.0 or higher.

AEs will be graded according to the National Cancer Institute Common Terminology Criteria for Adverse Events (NCI CTCAE) version 5.0.

In summaries by SOC and/or PT, adverse events will be sorted by decreasing frequency within each SOC and/or PT according to the highest subject number in Cohort A.

AEs will be classified as pre-treatment AEs or treatment-emergent adverse events (TEAEs) defined as follows:

Pre-treatment AE: any AE that started after study enrollment (ICF signed) and before the first dose date of study medication.

TEAE: any AE that was newly developed at or after the first dose date of study drug.

Related AE: AE will be defined as related if causality is either ‘definitely related’, ‘probably related’, ‘possibly related’ or missing.

Details for imputing missing or partial start dates of adverse events are described in section 7.2.2.

AE summary tables listed below will be presented:

- All TEAEs.
- All related TEAEs.
- TEAEs by maximum severity.

Final Analysis Statistical Analysis Plan (SAP)

- Serious TEAEs.
- Non-serious TEAEs.
- Related serious TEAEs.
- Related TEAEs by maximum severity.
- TEAEs with NCI CTCAE grades ≥ 3 .
- Related TEAEs of NCI CTCAE grades ≥ 3 .
- Important medical events (IMEs) (IMEs include only TEAEs):
 - Infusion-related reactions (IRRs).
 - Hepatic TEAEs (selecting events within “Drug related hepatic disorders - comprehensive search” Standardized MedDRA Queries (SMQ)).
 - Other IMEs (ie, SAEs with “Other important medical event” reason).
- Frequency of IRRs by maximum severity and visit.
- TEAEs leading to interruptions or modifications of study drug (action taken as “Drug reduced”, “Drug interrupted”, Drug delayed”, “Treatment held”).
- TEAEs leading to premature discontinuation of study drug (action taken as “Drug discontinued”).
- AEs leading to death.
- Related AEs leading to death.
- Frequent non-serious TEAEs (SOCs or PTs with at least 5% of subjects within the cohort).
- Glucocorticoid/Corticosteroid premedications (Yes/No) and frequency of IRR by maximum severity and visit.

All AEs will be summarized by MedDRA SOC, PT and cohort using frequency counts and percentages (ie, number and percentage of subjects with an event). In addition, an overall summary for the categories above will be prepared by cohort.

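### Same-day drugs given after an infusion has started can count as premedication, because the SAP's date-and-indication rule has no before-start condition

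*SAP*

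**What the plan says.** SAP 8.5.2 opens with the intended exposure: "The following medications taken before each AFM13 study drug administration will be listed and summarized". The concomitant-medication pages are not tied to visits, so the SAP gives a linking rule: "If premedication start date = Cycle X Day Y drug administration, the medication will be associated to the visit Cycle X Day Y". It then adds a second condition: "To be considered as a premedication, the indication of use should be “Other” or “Condition under study” or “Prophylaxis". For drugs entered as a single once-weekly line, the link is made "if the medication intake dates include the study drug administration date". None of these conditions uses clock time or asks whether the drug came before the infusion.

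For the antihistamine, analgesic and corticosteroid categories there is a second source. The sponsor supplies drug lists, but "this will be also based on the study drug administration CRF page questions relative to antihistamine, acetaminophen and dexamethasone (or equivalent steroid) intakes". The SAP does not say which source prevails when they disagree.

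The resulting flags feed two displays:

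- **SAP 8.5.2:** "To evaluate the relationship between dose intakes and pre-medications, an overall shift table will be generated". It counts infusions by whether they were interrupted and by antihistamine, analgesic and corticosteroid intake.
- **SAP 8.7.1:** "Glucocorticoid/Corticosteroid premedications (Yes/No) and frequency of IRR by maximum severity and visit".

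**The concern.** The definition concerns drugs given before the infusion, while the linking rule also admits drugs given later on the same day. The indication filter narrows this gap but does not close it. A steroid, antihistamine or analgesic given during an interruption, before the infusion is restarted, can reasonably be entered as 'Prophylaxis' or 'Other'. That infusion is then labelled premedicated because it was interrupted.

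This is not random misclassification. It moves infusions with an event from 'No' to 'Yes' and leaves event-free infusions where they are. The 'Yes' group then looks worse and the 'No' group better than they are, so a real benefit of premedication could be hidden.

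The question matters in this programme. Infusion-related reactions occurred in 28 of 30 patients (93.3%) in AFM13-103, given with pembrolizumab (Protocol 1.3.3.3). In the present study, persistent reactions in a responder are the condition for the every-other-week schedule (SAP 3.3).

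**Working it through.** **Step 1: the rules side by side.**

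| Item | Uses date | Uses time | Other condition |
|---|---|---|---|
| Definition of premedication (SAP 8.5.2) | – | before infusion | – |
| Same-day link (SAP 8.5.2) | yes | no | one of three indications |
| Once-weekly link (SAP 8.5.2) | yes, date range | no | – |
| Reaction-to-visit link (SAP 8.7.1) | yes | yes, 24-hour window | – |

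The reaction is placed by date and time, but the steroid cross-tabulated with it is not.

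**Step 2: size.** The documents give no figure for this point, so there is nothing to reproduce. Both illustrations below rest on assumed inputs and use the per-infusion interruption table.

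*Illustration A: no true association.* Let p be the share of infusions truly premedicated, i the interruption rate, g the chance that an interrupted, non-premedicated infusion is followed by a same-day drug of the class, and q the chance that this drug's indication passes the filter. Put f = g × q.

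- Rate in 'Yes' = i[p + (1−p)f] / {p(1−i) + i[p + (1−p)f]}
- Rate in 'No' = i(1−p)(1−f) / {(1−p)(1−i) + i(1−p)(1−f)}

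Example with p = 0.8, i = 0.1, g = 0.5, q = 0.25, so f = 0.125:

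- 'Yes': 0.0825 / (0.72 + 0.0825) = 10.3%
- 'No': 0.0175 / (0.18 + 0.0175) = 8.9%
- Ratio: 1.16, where the truth is 1.00

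Apparent ratio with g = 0.5 throughout:

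| p | i | q = 0 | q = 10% | q = 25% | q = 50% | q = 100% |
|---|---|---|---|---|---|---|
| 50% | 10% | 1.00 | 1.09 | 1.25 | 1.59 | 2.71 |
| 50% | 30% | 1.00 | 1.07 | 1.19 | 1.43 | 2.22 |
| 80% | 10% | 1.00 | 1.06 | 1.16 | 1.37 | 2.11 |
| 80% | 30% | 1.00 | 1.05 | 1.12 | 1.29 | 1.84 |

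The last column is what a rule with no indication filter would give. The first is what a filter that caught every such drug would give.

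*Illustration B: a true benefit.* Take 1,000 infusions. Of 800 truly premedicated, 80 (10%) are interrupted; of 200 not premedicated, 40 (20%) are. If m = 40f infusions move from 'No' to 'Yes', the table shows (80 + m)/(800 + m) against (40 − m)/(200 − m).

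| f | m | 'Yes' | 'No' |
|---|---|---|---|
| 0 | 0 | 10.0% | 20.0% |
| 10% | 4 | 84/804 = 10.4% | 36/196 = 18.4% |
| 25% | 10 | 90/810 = 11.1% | 30/190 = 15.8% |
| 50% | 20 | 100/820 = 12.2% | 20/180 = 11.1% |

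With g = 0.5, f = 25% requires q = 50%, and f = 50% requires that every such drug pass the filter. The last row is therefore an extreme case.

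**The case against.** The strongest reply is that the rule is better protected than it looks. A reader might infer that drugs are matched by calendar date alone; the indication condition contradicts that. If sites record rescue drugs as treatment of an adverse event, q is near zero and so is the bias. All three classes in the shift table also have a question on the visit-linked dosing page, and 'also based on' does not have to mean that a date-matched record overrides a 'No' there.

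Much is also out of view: the CRF indication list, the premedication section of the protocol (6.5) and SAP section 7 on derived variables and dates. A timing rule could stand in section 7. The displays are descriptive: SAP 8.7 plans no test for safety data, and none is specified for the shift table. Premedication is not randomised, so even a perfectly timed flag would be confounded by reaction history.

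Most of this stands as a limit on size. It does not remove the point. The readable rule still lacks a before-start condition, the filter admits two codes that suit a drug given before a restart, and no precedence between sources is stated. Confounding is a reason for cautious reading, not for adding an outcome-dependent error.

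**Conclusion.** The point holds as a minor one. As written, SAP 8.5.2 can count a same-day drug given after infusion start as premedication when its indication is coded 'Prophylaxis' or 'Other'. The resulting error depends on the outcome and tends to make premedication look associated with interruptions and reactions.

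How large it is cannot be read from the documents. In Illustration A the spurious ratio runs from 1.05 to 1.59 for q between 10% and 50%. All inputs are assumed, including that half of interrupted, non-premedicated infusions are followed by such a drug.

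Four stronger readings are not supported:

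- **The planned tables will lose or reverse a real difference.** That needs a high rate of miscoding, for which the documents give no evidence.
- **Antihistamines and analgesics distort the reaction table.** That table uses corticosteroids only; the other two flags reach only the interruption table.
- **The once-weekly wording biases these tables for subjects on every-other-week dosing.** A line entered with another recurring frequency would be linked only to its first date. This matters mainly for NSAIDs and 'other' drugs, which have no stated dosing-page question and enter neither cross-table.
- **The efficacy result is touched.** The response rate and its test do not use these flags.

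**What to change.** For the antihistamine, analgesic and glucocorticoid flags in the two tables:

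1. Let the answers on the study drug administration CRF page decide. First confirm that those questions refer to drugs given before the infusion; their exact wording is not visible.
2. Let a concomitant-medication record set a flag to 'Yes' only when its recorded start time is before infusion start.
3. Put date-matched records without a time in a separate 'timing unknown' category. Do this for every infusion, whether or not a reaction or interruption occurred. Dropping untimed records only on days with an event would define exposure by outcome and repeat the error in the other direction.
4. Add a sensitivity version of each table with 'timing unknown' counted as 'Yes'.

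As a minor addition, for the by-visit summary only, extend the repeat-record rule from once weekly to any recurring frequency, applied to the infusion dates that the frequency implies.

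The cost is SAP wording, some programming and two sensitivity tables. The main change uses CRF questions that the SAP already cites. Whether concomitant-medication start times are collected is not visible; if they are not, step 2 adds nothing and those records fall under step 3. The downside is that some true premedication not asked about on the dosing page, such as analgesics other than acetaminophen and possibly H2 antagonists, moves to 'timing unknown'.
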